#### Data

Data collected and processed as part of the study will be secured and managed as outlined in the data management section below. Participants will be advised that recordings of the Focus Groups (audio and video) will be made and that this will include identifiable information (especially in the case of video). They will be asked to provide explicit consent for this. Any incidents relating to processing, storage or sharing of data are not foreseen, however should these occur, they will be reported to Sponsor and managed as per the Newcastle University Research Data Management Policy.

ETHICAL AND REGULATORY CONSIDERATIONS

Regulatory Compliance and Research Ethics Committee Review and

**Reports** 

The study will be conducted in accordance with GCP. The Chief Investigator (also the

Principal Investigator) will obtain a favourable ethical opinion from an NHS Research

Ethics Committee (REC) prior to the start of the study. All parties will conduct the

study in accordance with this ethical opinion.

An agreement between Sponsor and each participating NHS PIC will be put in place,

and confirmation from each PIC of agreement to their activity, will also be obtained

prior to the start of recruitment via this method.

An annual progress report will be submitted each year to the REC by the CI until the

end of the study. This report will be submitted within 30 days of the anniversary date

on which the original favourable ethical opinion was granted.

The CI will notify the REC of the early termination or end of study in accordance with

the required timelines.

**Amendments** 

It is the responsibility of the Research Sponsor to determine if an amendment is

substantial or not and study procedures must not be changed without the mutual

agreement of the CI and Sponsor. Substantial amendments will be submitted to the

REC and HRA and will not be implemented until approvals from both are in place.

Non-substantial amendments will be submitted to the Health Research Authority

(HRA) and will not be implemented until authorisation is received.

Notification of Serious Breaches to GCP and/or the Protocol

A serious breach is a breach which is likely to effect to a significant degree –

a) the safety or physical or mental integrity of the subjects of the study; or

b) the scientific value of the study

The sponsor must be notified immediately of any incident that may be classified as a

serious breach.

The Chief Investigator will also, on behalf of Sponsor, notify the NHS REC within the

required timelines (7 days of awareness of the serious breach).

**Data Management** 

Source Data

Source data for this study will consist of recorded Focus Groups (audio and video

files), the transcripts from these, and paper worksheets recording demographic details

and medical history.

Focus Group: Access, Recordings and Transcription

Focus Groups will be recorded via computer video-conferencing software (e.g., MS

Teams or Zoom) or using a digital recording device.

Access to the virtual meetings will be controlled via password or secure link that will

be provided to participants via email.

Any video-conferencing software will be used under a Newcastle University licence.

The recordings will be stored via the video-conferencing system in a secure area of

the system, accessible to authorised Newcastle University staff only. Audio recordings

from in-person sessions will be downloaded from the recording device directly onto a

restricted access shared drive on Newcastle University servers accessible only to the

research team.

In order to protect confidentially as much as possible, during Focus Groups,

participants will be referred to by first name only.

Recordings will be transcribed as soon as possible after the session. Transcriptions

will be made by an authorised member of the study team at Newcastle University.

During transcription of recordings, all names will be removed and participants will be

referred to by unique study ID.

Names of any hospitals and clinicians will also be removed, however these may be

coded by institution type e.g. primary care provider, secondary or tertiary care service.

Transcriptions will be stored on a secure shared drive on Newcastle University servers

which is accessible to the study team only.

All recordings will be deleted following transcription. A separate Data Protection SOP

for the study outlines the security arrangements for the storage and management of

Focus Group recordings and transcripts and study data.

Collection of Demographic and Medical History Data

Participants will be asked to provide limited demographic and medical history details

(including details of genetic diagnosis). This will be recorded on paper worksheets

(completed by the participant or a member of the study team during discussion with

them). Completed worksheets will be returned to the study team in person or via email,

however will be de-identified (referring to the participant by a unique study ID rather

than by name). Completed worksheets will be held in the combined study Trial Master

File/Investigator Site File (TMF/ISF) on paper and in a secure study shared drive on

Newcastle University servers.

Identifiable data: Consent Forms, Study Enrolment Logs and Participant Contact

**Details** 

A number of pieces of identifiable data will be collected and stored. However, these

details will not be used in the analysis or dissemination of study results and will not be

shared outside the research team.

Completed study consent forms will be held in the combined TMF/ISF. This will be

securely stored in the clinical trials office within the Wellcome Centre for Mitochondrial

Research, Newcastle University.

An enrolment log recording the names of all study participants and linking participant

name to each participant's unique study ID will also be held in the TMF/ISF.

A list of preferred participant contact details (e.g. containing participant name, email

address, postal address (if required) and telephone number) will also be retained in

the TMF/ISF.

These identifiable details will be used to arrange focus group/interview appointments,

to arrange travel and payment of expenses, and to provide any relevant updates to

participants during the study.

**Evaluation Data** 

At the end of their participation participants will be invited to provide feedback on their

experienced of being involved in the study. This will be via completion of a survey

(either online or on paper). The survey will be optional and will be anonymous

(participants will not be required to provide their name or study ID). Evaluation data

will be stored on paper in the TMF/ISF or online via Newcastle University Servers.

Data Handling and Governance

The study will comply with all relevant data protection legislation. A Data Protection

Impact Assessment (DPIA) will be completed and approved by the Sponsor and Data

Controller (Newcastle University) prior to the start of data collection.

Study data (from worksheets and from Focus Group transcription) will be collated by

a member of the research team at Newcastle University. It is anticipated that Excel or

a similar programme will be used to hold collated data for analysis (which will be

retained in a secure area on Newcastle University servers). Only members of the study

team will have direct access to the data, as approved by the study Chief Investigator.

For analyses, participants will be identified via their study ID, no direct personal

identifiers will be used.

Upon completion of the study and all analyses, the TMF/ISF, and associated electronic

study documentation will be archived in accordance with Newcastle University

procedures for a minimum of 10 years (as per the Newcastle University

Research Data Management Policy Principles & Code of Good Practice).

Access to Data and Data Sharing

Direct access to study data including source data contained on Newcastle University

servers and personal identifiable data contained in the TMF/ISF will be granted to

authorised representatives of the Sponsor or regulatory authorities for the purposes of

monitoring, audit or inspection. Consent for this will be obtained from participants

during recruitment.

Following completion of the study, pseudo-anonymised sets of data may be made

available for 3rd party research purposes with the appropriate data transfer

procedures. Consent for this will be obtained from all participants.

**Insurance and Indemnity** 

Newcastle University has in place a Public Liability Policy which provides cover to the

University for harm which comes about through the University's, or its staff's,

negligence in relation to the design, management or conduct of the study. No

arrangements for cover for non-negligent harm will be included.

Participant Reimbursement for Time

In recognition that participants will be required to give up their time for participating,

they will be offered reimbursement in the form of a voucher. This will recognise the

time involved in preparing for, attending the Focus Group and for any evaluation

activities following the Focus Group.

COMMUNICATION AND DISSEMINATION OF RESULTS

Findings from the study may be reported at local, national and international meetings,

on social media platforms (including [but not limited to, Newcastle University,

Wellcome Centre for Mitochondrial Research, charity partners], as well as in peer-

reviewed journals. Study participants will be advised in the Participant Information

Sheet that they can contact the study team to request a lay summary of the overall

research results once the study is complete.

EXPLORE Protocol Version: 2.0, 2022-09-23

Page 24 of 31

# APPENDIX 1: SEMI-STRUCTURED MODERATOR INTERVIEW GUIDE

## 1. Experience leading to the point of diagnosis of mitochondrial disease.

### Life before the diagnosis of mitochondrial disease:

Had you/the person you care(d) for ever heard of mitochondrial disease?
 (did you know it was a genetic disorder; were you aware that you had a family history)?

### Symptoms before presentation of stroke-like episode:

- Did you/the person you care(d) for have any symptoms associated with mitochondrial disease (e.g. deafness, diabetes, muscle weakness) prior to the first occurrence of an acute stroke-like episode?
- Were you informed about the risk and symptoms associated with strokelike episodes by the medical professionals? (this question is applicable only for those individuals who already had a genetic diagnosis of mitochondrial disease before developing stroke-like episodes)

## 2. Experience leading to the acute presentation of stroke-like episode.

### Diagnosis:

- How did you find the process of reaching the diagnosis of stroke-like episode?
- Did you feel that you were provided sufficient information about stroke-like episodes by the medical professionals (e.g. GP, hospital specialist, allied health personnel)?
- Following your diagnosis of stroke-like episodes (or that of the person you care(d) for), have you tried to obtain more information? (i.e. experience from other family member(s) similarly affected, published medical literature, patient organisation/s, social media/ patient forum or other sources)?
- If you/the person you care(d) for were to have a further hospital admission for a suspected stroke-like episode, do you feel confident to recognise the relevant symptoms?

### Management:

- Reflecting on your most recent admission with stroke-like episode/s (or that of the person you care(d) for), what was the length of stay in hospital? Did you feel that the hospital team understand the condition?
- Reflecting on your most recent admission with stroke-like episode/s (or that of the person you care(d) for), what treatments have you been offered? (antiepileptic drugs, L-arginine and other)
- Reflecting on your most recent admission with stroke-like episode/s (or that of the person you care(d) for), how would you describe the overall experience?

### 3. Experience leading to post-acute event.

#### Rehabilitation:

- After you/the person you care(d) for has been discharged from hospital, do you feel you received appropriate rehabilitation and support in the community?
- Have you or the person you care(d) for ever been admitted to a respite care facility? If so, what was the length of stay?

### Follow up arrangement:

- In general, how well do you feel that you are supported by your local clinical services (e.g. general practitioners, general neurologist, clinical geneticist, physiotherapist) following the discharge from the hospital and/or rehabilitation service?
- Have you attended one of the Highly Specialised Service for rare mitochondrial disorders (Newcastle, London and Oxford)? What has been your experience?

### 4. Impact of stroke-like episodes on various aspects of life.

### **Seizures**

- How do you/the person you care(d) find living with seizures following strokelike episodes?
- How do you/the person you care(d) find taking anti-epileptic medications?

### Cognitive:

 Have you/the person you care(d) for suffered from persistent/progressive cognitive impairment (e.g. reduced concentration span, short-term memory deficits, difficulties to perform visual-spatial tasks, language deficits)? What are the impacts on the activities of daily living?

### **Physical impact:**

 Have you/the person you care(d) for experienced physical symptoms (e.g. muscle weakness, fatigue) following the stroke-like episodes? What are the impacts on the activities of daily living?

### **Psychological impact:**

 What do you feel is the psychological impact you/the person you care(d) for following stroke-like episode(s)?

### Impact on relationships:

• As a result of mitochondrial stroke-like episodes, has the relationship between you/the person you care(d) for, changed (for example, with family, parents, partners, siblings, children; friends, acquaintances or strangers)?

### Impact on work/studies:

 Have you/the person you care(d) for had to adjust your work or study as a result of mitochondrial stroke-like episodes (for example, reduced professional commitments, stopped working or education)?

### Impact on recreation:

 Have you/the person you care(d) for had a change in the type or time spent in recreational activities as a result of mitochondrial stroke-like episodes? (for example, given up hobbies).

### **Financial impact:**

- As a result of mitochondrial stroke-like episodes, have you/the person you care(d) for faced financial challenges as a result? (for example, loss or reduction of personal income due to employment circumstances/reduced job activity; purchase of medications or additional out of pocket expenses).
- Have you/the person you care(d) for encountered any difficulties navigating the social welfare system?

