### **OBJECTIVES**

### **Primary Objectives:**

1. Explore patients' and their caregivers' ability to recognise SLE symptoms;

2. Explore the experiences of patients and their caregivers in accessing medical help when an SLE is suspected;

3. Explore the experiences of patients and their caregivers regarding hospital admission for a SLE/suspected SLE;

4. Explore if the patient has had any physical and cognitive rehabilitation following an acute admission for a SLE;

5. Explore the long-term impacts of SLEs on activities of daily living and quality of life in patients and their caregivers.

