**STATISTICS** 

**Quantitative Analyses** 

Descriptive statistics will be used to analyse the demographic characteristics of the

patient and caregiver participants. The Focus Groups will provide an opportunity to

gather insight into particular topics. These findings will be investigated for themes and

ideas for future quantitative approaches, however, will not be interpreted for

statistically significant results in the current study.

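### Fourteen of the 25 interview-guide items are closed with no written open prompt; four impact items are also framed only by loss or difficulty, and none asks how people manage

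*Protocol*

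**What the plan says.** The fifth primary objective is to "Explore the long-term impacts of SLEs on activities of daily living and quality of life in patients and their caregivers". Under Statistics, Quantitative Analyses, the focus group findings are to be examined for themes and "ideas for future quantitative approaches, however, will not be interpreted for" statistical significance. Qualitative Analyses plans coding into themes with the framework in Appendix 2. The second secondary objective is to use the data to help write quantitative survey questions.

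Appendix 1 supplies the questions. In its impact section:

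- The financial item asks whether the participant or the person cared for has "faced financial challenges as a result? (for example, loss or reduction of personal income due to employment circumstances/reduced job activity". A second item under that heading asks only about difficulties with the welfare system.
- The work/studies item asks about having to adjust, with the examples "for example, reduced professional commitments, stopped working or education".
- The recreation item asks about a change in "recreational activities as a result of mitochondrial stroke-like episodes? (for example, given up hobbies".
- The cognitive item asks whether the person has "suffered from persistent/progressive cognitive impairment", but then asks openly about the effect on daily living. The physical item has the same structure.

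The Risks section says that participants receive the focus group schedule beforehand and that moderators will be experienced. It identifies that schedule as the Appendix 1 guide.

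**The concern.** The objectives are exploratory and the analysis is thematic, so the data need to be accounts in the participants' own terms. A bare yes or no gives a coder little to work with. Where a closed question also offers only losses as examples, the easiest reply is to agree with what was listed. Adaptation, absence of impact or improvement then has to be volunteered.

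Two things are at stake. The first is the balance of the evidence for objective 5. The second is the later survey: items drafted from a one-sided account would carry the slant forward.

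**Working it through.** The Protocol states no item count, and no sample-size or error-rate formula applies. The check is a count of Appendix 1, taking each bullet as one item. An item is *open* if any part invites an account, *closed* if it contains a yes/no question and no open part, and *factual* if it only asks for a fact.

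| Appendix 1 section | Items | Open | Closed | Factual only |
|---|---|---|---|---|
| 1. Up to diagnosis of mitochondrial disease | 3 | 0 | 3 | 0 |
| 2. Acute presentation | 7 | 2 | 4 | 1 |
| 3. Post-acute | 4 | 2 | 2 | 0 |
| 4. Impact | 10 | 5 | 5 | 0 |
| 5. Other | 1 | 1 | 0 | 0 |
| **Total** | **25** | **10** | **14** | **1** |

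Closed: 14/25 = 56%. Open: 10/25 = 40%, made up of seven purely open items and three yes/no items with an open follow-up (Highly Specialised Service, cognitive, physical).

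Two of the 14 also contain a factual question about length of stay: the first Management item and the respite-care item. Neither addition invites an account. Leaving both out gives 14 − 2 = 12, or 12/25 = 48%.

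The ten impact items, by form and framing:

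| Item | Form | Loss or difficulty only, in stem or examples? |
|---|---|---|
| Living with seizures | open | no |
| Taking anti-epileptic medication | open | no |
| Cognitive | yes/no, then open | yes |
| Physical | yes/no, then open | yes |
| Psychological | open | no |
| Relationships | closed | no (asks about change; examples are people) |
| Work/studies | closed | yes, in the examples |
| Recreation | closed | yes, in its single example; stem neutral |
| Financial challenges | closed | yes, in stem and examples |
| Social welfare | closed | yes, in the stem |

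Six of the ten are loss-framed. Two of those six have an open follow-up, so 6 − 2 = 4 are both closed and loss-framed. That is 4/10 of the impact items and 4/25 = 16% of the guide.

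The guide was then set against the coding frame in Appendix 2:

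- Strategies/management is a code under cognitive, physical, psychological, relationships, work/studies and recreation, which is six of eight impact themes (not seizures or financial). No guide item asks what the patient or caregiver does to manage. The nearest items ask about seeking information, support from services, or support wanted in future.
- The theme on life before diagnosis has codes for identity, employment or education, daily living, and hopes and plans. The only guide item under that heading asks whether the person had "ever heard of mitochondrial disease", with bracketed prompts that are also yes/no.

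**The case against.** The strongest reply is that this is a semi-structured guide and not a questionnaire. Groups of four or five have up to 180 minutes, which is 180/25 = 7.2 minutes per item before breaks and far more than yes/no answers need. Moderators are to be experienced, and the Appendix 2 codes suggest that the team expects talk well beyond the literal questions. Closed openers can be legitimate: objective 4 itself asks whether rehabilitation took place, and closed items may help in drafting survey questions. Sending the schedule in advance is a safeguard for informed choice on emotive topics.

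Most of this stands, and it limits the consequence to a risk. It does not remove the point. No probes are written for the closed items, so what is drawn out may vary between the planned six groups. A coding frame that expects coping strategies, beside a guide that never asks for them, is a mismatch between the two appendices. The advance schedule serves its purpose, but it also means that the listed losses reach participants before discussion starts.

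A reader might go further and infer that the impact section names only losses, or that the study will collect agreement with suggested harms in place of experience. The documents do not support either reading. The seizure, medication, psychological and relationship items suggest no loss as the answer, and half of the impact items allow an open reply. Most of the 14 closed items suggest no harm. For example, "Were you informed about the risk and symptoms associated with strokelike episodes by the medical professionals" is closed but does not steer towards loss. The 56% therefore measures closed wording and not loss bias.

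**Conclusion.** The point holds as a modest, inexpensive improvement. Fourteen of 25 items (12 on the strictest reading) have no written open prompt; four of the ten impact items combine that with loss-only framing; and no item asks about the coping content that six of eight impact themes are set up to code. The likely effect is a less balanced account for objective 5 and for survey items built on it. Its size cannot be estimated from the Protocol, because it depends on how far moderators probe beyond the written text. The counts rest on treating each bullet as one item and on the classification shown above.

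**What to change.** Amend Appendix 1 before the first session:

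1. Reword the work/studies, recreation, financial and social welfare items as neutral open questions, for example *How, if at all, has your work or study changed, for better, for worse or not at all?* Alternatively, balance their examples.
2. Add a neutral follow-up to the other ten closed items, such as *Can you tell us about that?*
3. Add *What, if anything, has helped you manage this?* to the six impact topics that carry a Strategies/management code.

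The schedule sent to participants should carry the same wording. The cost is a wording amendment, handled as the Amendments section requires, and somewhat longer answers within the 180-minute session. No extra participants, visits or data fields are needed.
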